10.4. Appendix 4: Derived and Transformed Data

10.4.1. General

Multiple Measurements at One Analysis Time Point

 • Mean of the measurements will be calculated and used in any derivation of summary statistics but if listed, all data will be presented. • The worst finding/interpretation associated with multiple measurements as the finding/interpretation for that time point. • Participants having both High and Low values for Normal Ranges at any post-baseline visit for safety parameters will be counted in both the High and Low categories of “Any visit post-baseline” row of related summary tables. This will also be applicable to relevant Potential Clinical Importance summary tables.
Study Day

 • Calculated as the number of days from Dose Date on Period 1 Day 1: 
 • Assessment Date = Missing → Study Day = Missing • Assessment Date < Dose Date on Period 1 Day 1 → Study Day = Assessment Date – Dose Date on Period 1 Day 1 • Assessment Date >= Dose Date on Period 1 Day 1 → Study Day = Assessment Date – Dose Date on Period 1 Day 1 + 1
Period Day

 • Calculated as the number of days from First Dose Date for the respective period: 
 • Assessment Date = Missing → Period Day = Missing • Assessment Date < Dose Date on Period 1 Day 1 → Period Day = Assessment Date – Dose Date on Period 1 Day 1 • Dose Date on Period 1 Day 1 <= Assessment Date < Dose Date on Period 2 Day 1 → Period Day = Assessment Date – Dose Date on Period 1 Day 1 + 1 • Dose Date on Period 2 Day 1 <= Assessment Date < Dose Date on Period 3 Day 1 → Period Day = Assessment Date – Dose Date on Period 2 Day 1 + 1 • Dose Date on Period 3 Day 1 <= Assessment Date < Dose Date on Period 4 Day 1 → Period Day = Assessment Date – Dose Date on Period 3 Day 1 + 1 • Assessment Date >= Dose Date on Period 4 Day 1 → Period Day = Assessment Date – Dose Date on Period 4 Day 1 + 1

10.4.2. Study Population

Age

 • GSK standard IDSL algorithms will be used for calculating age where birth date will be imputed as follows: 
 ○ Any participant with a missing day will have this imputed as day ‘15’. ○ Any participant with a missing day and month will have this imputed as ‘30th June’. • Birth date will be presented in listings as ‘YYYY’.
Body Mass Index (BMI)

 • Calculated as Weight (kg) / [Height (m)²]

10.4.3. Safety

Adverse Events
AEs of Special Interest

 • QT prolongation • Gastrointestinal intolerability/toxicity • Psychiatric events • Nervous system disorders

12-Lead Electrocardiograms
QTcB Interval

 • QTc using the Bazett formula (QTcB) interval in msec will be calculated using QT interval (msec) and RR (msec) as $QT_{cB} = \frac{QT}{\sqrt{\frac{RR}{1000}}}$ 
where RR interval in msec is calculated using QT interval (msec) and QTcF interval (msec) as
 $RR = \left(\frac{QT}{QT_{cF}}\right)^3 \times 1000$

10.5. Appendix 5: Reporting Standards for Missing Data

10.5.1. Premature Withdrawals

Element	Reporting Detail
General	
 Participant study completion (i.e. as specified in the protocol) was defined as the participant had completed all phases of the study including the final date on which data were or are expected to be collected. Withdrawn participants were not replaced in the study. All available data from participants who were withdrawn from the study will be listed and all available planned data will be included in summary tables and figures, unless otherwise specified.

10.5.2. Handling of Missing Data

Element	Reporting Detail
General	
 Missing data occurs when any requested data is not provided, leading to blank fields on the collection instrument: 
 These data will be indicated by the use of a “blank” in participant listing displays. Unless all data for a specific visit are missing in which case the data is excluded from the table. Answers such as “Not applicable” and “Not evaluable” are not considered to be missing data and should be displayed as such.
Outliers	
 Any participants excluded from the summaries and/or statistical analyses will be documented along with the reason for exclusion in the CSR.

10.5.2.1. Handling of Missing and Partial Dates

Element	Reporting Detail
General	
 Partial dates will be displayed as captured in participant listing displays.
Adverse Events	
 The eCRF allows for the possibility of partial dates (i.e., only month and year) to be recorded for AE start and end dates; that is, the day of the month may be missing. In such a case, the following conventions will be applied for calculating the time to onset and the duration of the event: 
 Missing Start Day: First of the month will be used unless this is before the start date of study treatment; in this case the study treatment start date will be used and hence the event is considered On-treatment as per Appendix 2: Study Phases and Treatment Emergent Adverse Events. Missing Stop Day: Last day of the month will be used, unless this is after the stop date of study treatment; in this case the study treatment stop date will be used. Completely missing start or end dates will remain missing, with no imputation applied. Consequently, time to onset and duration of such events will be missing.
Concomitant Medications	
 Partial dates for any concomitant medications recorded in the eCRF will be imputed using the following convention: 
 If the partial date is a start date, a '01' will be used for the day and 'Jan' will be used for the month If the partial date is a stop date, a '28/29/30/31' will be used for the day (dependent on the month and year) and 'Dec' will be used for the month. The recorded partial date will be displayed in listings.

CONFIDENTIAL

209713

10.6. Appendix 6: Division of AIDS (DAIDS) Table for Grading the Severity of Adult and Pediatric Adverse Events

10.6.1. Laboratory Values

Laboratory abnormalities will be graded according to the DAIDS grading table Version 2.1, July 2017. Laboratory results are converted to use SI units; only the numeric part of the criteria will be used. If for a laboratory parameter there are multiple grades sharing the same criteria, the maximum grade will be used.

HEMATOLOGY				
	Grade 1	Grade 2	Grade 3	Grade 4
Absolute Lymphocyte Count, Low (cell/mm ³ ; cells/L) > 5 years of age (not HIV infected)	600 to < 650 0.600 × 10 ⁹ to < 0.650 × 10 ⁹	500 to < 600 0.500 × 10 ⁹ to < 0.600 × 10 ⁹	350 to < 500 0.350 × 10 ⁹ to < 0.500 × 10 ⁹	< 350 < 0.350 × 10 ⁹
Absolute Neutrophil Count, Low (cells/mm ³ ; cells/L) > 7 days of age	800 to 1,000 0.800 × 10 ⁹ to 1.000 × 10 ⁹	600 to 799 0.600 × 10 ⁹ to 0.799 × 10 ⁹	400 to 599 0.400 × 10 ⁹ to 0.599 × 10 ⁹	< 400 < 0.400 × 10 ⁹
Hemoglobin, Low (g/dL; mmol/L) ≥ 13 years of age (male only)	10.0 to 10.9 6.19 to 6.76	9.0 to < 10.0 5.57 to < 6.19	7.0 to < 9.0 4.34 to < 5.57	< 7.0 < 4.34
Hemoglobin, Low (g/dL; mmol/L) ≥ 13 years of age (female only)	9.5 to 10.4 5.88 to 6.48	8.5 to < 9.5 5.25 to < 5.88	6.5 to < 8.5 4.03 to < 5.25	< 6.5 < 4.03
Platelets, Decreased (cells/mm ³ ; cells/L)	100,000 to < 125,000 100.000 × 10 ⁹ to < 125.000 × 10 ⁹	50,000 to < 100,000 50.000 × 10 ⁹ to < 100.000 × 10 ⁹	25,000 to < 50,000 25.000 × 10 ⁹ to < 50.000 × 10 ⁹	< 25,000 < 25.000 × 10 ⁹
White Blood Cell, Decreased (cells/mm ³ ; cells/L) > 7 days of age	2,000 to 2,499 2.000 × 10 ⁹ to 2.499 × 10 ⁹	1,500 to 1,999 1.500 × 10 ⁹ to 1.999 × 10 ⁹	1,000 to 1,499 1.000 × 10 ⁹ to 1.499 × 10 ⁹	< 1,000 < 1.000 × 10 ⁹

CONFIDENTIAL

209713

Clinical Chemistry				
	Grade 1	Grade 2	Grade 3	Grade 4
Albumin, Low (g/dL; g/L)	3.0 to < LLN 30 to < LLN	≥ 2.0 to < 3.0 ≥ 20 to < 30	< 2.0 < 20	NA
Alkaline Phosphatase, High	1.25 to < 2.5 × ULN	2.5 to < 5.0 × ULN	5.0 to < 10.0 × ULN	≥ 10.0 × ULN
Alanine Aminotransferase, High	1.25 to < 2.5 × ULN	2.5 to < 5.0 × ULN	5.0 to < 10.0 × ULN	≥ 10.0 ULN
Amylase (Total), High	1.1 to < 1.5 × ULN	1.5 to < 3.0 × ULN	3.0 to < 5.0 × ULN	≥ 5.0 × ULN
Aspartate Aminotransferase, High	1.25 to < 2.5 × ULN	2.5 to < 5.0 × ULN	5.0 to < 10.0 × ULN	≥ 10.0 × ULN
Bicarbonate, Low (mEq/L; mmol/L)	16.0 to < LLN 16.0 to < LLN	11.0 to < 16.0 11.0 to < 16.0	8.0 to < 11.0 8.0 to < 11.0	< 8.0 < 8.0
Direct Bilirubin, High > 28 days of age	NA	NA	> ULN with other signs and symptoms of hepatotoxicity	> ULN with life-threatening consequences (e.g., signs and symptoms of liver failure)
Total Bilirubin, High > 28 days of age	1.1 to < 1.6 × ULN	1.6 to < 2.6 × ULN	2.6 to < 5.0 × ULN	≥ 5.0 × ULN
Calcium, High (mg/dL; mmol/L) ≥ 7 days of age	10.6 to < 11.5 2.65 to < 2.88	11.5 to < 12.5 2.88 to < 3.13	12.5 to < 13.5 3.13 to < 3.38	≥ 13.5 ≥ 3.38
Calcium, Low (mg/dL; mmol/L) ≥ 7 days of age	7.8 to < 8.4 1.95 to < 2.10	7.0 to < 7.8 1.75 to < 1.95	6.1 to < 7.0 1.53 to < 1.75	< 6.1 < 1.53
Creatine Kinase, High	3 to < 6 × ULN	6 to < 10 × ULN	10 to < 20 × ULN	≥ 20 × ULN
Creatinine, High Choose the method that selects for the higher grade	1.1 to 1.3 × ULN	> 1.3 to 1.8 × ULN OR Increase to 1.3 to < 1.5 × participant's baseline	> 1.8 to < 3.5 ULN OR Increase to 1.5 to < 2.0 × participant's baseline	≥ 3.5 × ULN OR Increase of ≥ 2.0 × participant's baseline
Glucose Fasting, High (mg/dL; mmol/L)	110 to 125 6.11 to < 6.95	> 125 to 250 6.95 to < 13.89	> 250 to 500 13.89 to < 27.75	≥ 500 ≥ 27.75
Glucose, Low (mg/dL; mmol/L) ≥ 1 month of age	55 to 64 3.05 to < 3.55	40 to < 55 2.22 to < 3.05	30 to < 40 1.67 to < 2.22	< 30 < 1.67
Lipase, High	1.1 to < 1.5 × ULN	1.5 to < 3.0 × ULN	3.0 to < 5.0 × ULN	≥ 5.0 × ULN
Cholesterol, Fasting, High (mg/dL; mmol/L) ≥ 18 years of age	200 to < 240 5.18 to < 6.19	240 to < 300 6.19 to < 7.77	≥ 300 ≥ 7.77	NA
Triglycerides, Fasting, High (mg/dL; mmol/L)	150 to 300 1.71 to 3.42	> 300 to 500 > 3.42 to 5.7	> 500 to < 1,000 > 5.7 to 11.4	> 1,000 > 11.4
Phosphate, Low (mg/dL; mmol/L) > 14 years of age	2.0 to < LLN 0.65 to < LLN	1.4 to < 2.0 0.45 to < 0.65	1.0 to < 1.4 0.32 to < 0.45	< 1.0 < 0.32

CONFIDENTIAL

209713

Clinical Chemistry				
	Grade 1	Grade 2	Grade 3	Grade 4
Potassium, High (mEq/L; mmol/L)	5.6 to < 6.0 5.6 to < 6.0	6.0 to < 6.5 6.0 to < 6.5	6.5 to < 7.0 6.5 to < 7.0	≥ 7.0 ≥ 7.0
Potassium, Low (mEq/L; mmol/L)	3.0 to < 3.4 3.0 to < 3.4	2.5 to < 3.0 2.5 to < 3.0	2.0 to < 2.5 2.0 to < 2.5	< 2.0 < 2.0
Sodium, High (mEq/L; mmol/L)	146 to < 150 146 to < 150	150 to < 154 150 to < 154	154 to < 160 154 to < 160	≥ 160 ≥ 160
Sodium, Low (mEq/L; mmol/L)	130 to < 135 130 to < 135	125 to < 130 125 to < 130	121 to < 125 121 to < 125	≤ 120 ≤ 120
Uric Acid, High (mEq/L; mmol/L)	7.5 to < 10.0 0.45 to < 0.59	10.0 to < 12.0 0.59 to < 0.71	12.0 to < 15.0 0.71 to < 0.89	≥ 15.0 ≥ 0.89

NA=not applicable; LLN = lower limit of normal; ULN=upper limit of normal.

Urinalysis				
	Grade 1	Grade 2	Grade 3	Grade 4
Glucose/Glycosuria (random collection tested by dipstick)	Trace to 1+ or ≤ 250 mg	2+ or > 250 to ≤ 500 mg	> 2+ or > 500 mg	NA
Protein/Proteinuria (random collection tested by dipstick)	1+	2+	3+ or higher	NA
Red Blood Cells (RBCs)/Hematuria (not to be reported based on dipstick findings or on blood believed to be of menstrual origin)	6 to < 10 RBCs per high power field	≥ 10 RBCs per high power field	Gross, with or without clots OR with RBC casts OR intervention indicated	Life-threatening consequences

NA=not applicable

CONFIDENTIAL

209713

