10.2. Appendix 2: Clinical Laboratory Tests

- The tests detailed in [Table 2](#) will be performed by the local laboratory.
- Protocol-specific requirements for inclusion or exclusion of participants are detailed in [Section 5](#) of the protocol.
- Additional tests may be performed at any time during the study as determined necessary by the investigator or required by local regulations.
- Pregnancy Testing
 - Refer to [Section 5.1](#) Inclusion Criteria for Screening pregnancy criteria.
 - Pregnancy testing (urine or serum as required by local regulations) should be conducted at the time points indicated in the SoA ([Section 1.3](#)).
 - Additional serum or urine pregnancy tests may be performed, as determined necessary by the investigator or required by local regulation, to establish the absence of pregnancy at any time during the participant's participation in the study.

Table 2 Protocol-Required Safety Laboratory Assessments

Laboratory Assessments	Parameters		
Hematology	Platelet Count Red Blood Cell Count Hemoglobin Hematocrit	Red Blood Cell Indices: Mean corpuscular volume Mean corpuscular hemoglobin	White blood cell count with differential: Neutrophils Lymphocytes Monocytes Eosinophils Basophils Absolute neutrophil count
Clinical Chemistry ¹	Blood urea nitrogen Creatinine Glucose (fasting) Potassium Sodium Calcium Chloride Phosphorus	Carbon dioxide Aspartate aminotransferase Alanine aminotransferase Gamma-glutamyl transferase Total and direct bilirubin Lactate dehydrogenase Total cholesterol Triglycerides	Total protein Albumin Globulin Anion gap Alkaline phosphatase Uric acid Creatine phosphokinase Serum lipase Serum amylase
Routine Urinalysis	
 • Specific gravity • pH, glucose, protein, blood, ketones, bilirubin, urobilinogen, nitrite, and leukocyte esterase by dipstick • Microscopic examination (if blood, leukocyte esterase, or protein is abnormal) 		

Laboratory Assessments	Parameters
Other Screening Tests	
 • Serology: HIV-1 and -2 antigen/antibody immunoassay, hepatitis B surface antigen, hepatitis C antibody • Alcohol, cotinine, and drug screen (to include at minimum amphetamines, barbiturates, cocaine, opiates, cannabinoids, and benzodiazepines) • Pregnancy ²

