8.2. Clinical Laboratory Analyses

Laboratory evaluations including the analyses of chemistry laboratory tests, hematology laboratory tests, urinalysis, and liver function tests will be based on GSK Core Data Standards and will be graded using the Division of AIDS (DAIDS) Table for Grading the Severity of Adult and Pediatric Adverse Events (Version 2.1, July 2017). The details of the planned displays are in [Appendix 9](#): List of Data Displays.

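### SAP 10.6.1 programs every direct bilirubin above ULN as Grade 4, a grade the printed DAIDS row does not give to an isolated elevation (minor; Listings 22 and 23 only)

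*SAP*

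**What the plan says.** SAP 8.2 says that laboratory evaluations, including liver function tests, are graded by DAIDS Version 2.1. SAP 10.6.1 repeats this: "Laboratory abnormalities will be graded according to the DAIDS grading table Version 2.1, July 2017". It then adds two rules for applying the table:

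- Rule 1: "Laboratory results are converted to use SI units; only the numeric part of the criteria will be used".
- Rule 2: "If for a laboratory parameter there are multiple grades sharing the same criteria, the maximum grade will be used".

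The direct bilirubin row printed below these rules has NA for Grades 1 and 2. Grade 3 is "> ULN with other signs and symptoms of hepatotoxicity". Grade 4 is "> ULN with life-threatening consequences (e.g., signs and symptoms of liver failure".

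The test is done routinely: the clinical chemistry panel in Protocol Appendix 2, Table 2, includes "Total and direct bilirubin". No exemption from the two rules is stated for this or any other row.

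**The concern.** In the printed row the laboratory value alone never earns a grade. What separates no grade, Grade 3 and Grade 4 is the clinical picture, and that is what Rule 1 discards. Rule 2 then resolves the resulting tie upwards. A well participant slightly above ULN would carry the top grade in the programmed data, and so would a participant who had only the Grade 3 clinical component.

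What is at stake is how a liver parameter is labelled in the participant-level listings. A reader of the study report who met a Grade 4 direct bilirubin would take it for a life-threatening laboratory event, when the data behind it may be one value just above the reference limit.

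**Working it through.** The plan states no figure on this point, so there is none to reproduce. The check applies the two rules to the printed rows and then traces where the programmed grade is used.

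**Step 1: direct bilirubin.** The inputs are the row and the two rules in SAP 10.6.1.

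| Grade | Printed criterion | After Rule 1 | After Rule 2 |
|---|---|---|---|
| 1 | NA | none | none |
| 2 | NA | none | none |
| 3 | above ULN, plus other hepatotoxicity findings | > ULN | never assigned |
| 4 | above ULN, plus life-threatening consequences | > ULN | every value > ULN |

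For an isolated value with no clinical finding:

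| Value | Printed row | SAP rules |
|---|---|---|
| 0.90 or 1.00 × ULN | no grade | no grade |
| 1.01, 1.5, 3 or 10 × ULN | no grade | Grade 4 |

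**Step 2: other rows.** The numeric part of each of the 32 rows was coded (6 hematology, 23 chemistry, 3 urinalysis) and searched for grades sharing a criterion. Direct bilirubin is the only row in which two grades share a non-empty one. In hematuria, Grade 3 ("Gross, with or without clots OR with RBC casts OR intervention indicated") and Grade 4 have no numeric part, so both are empty after Rule 1 and no value triggers either. Creatinine has alternative criteria based on ULN and on the participant's baseline, but they are not identical between grades, and the row carries its own instruction to take the higher grade.

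**Step 3: where the grade goes.** From the list of displays in SAP Appendix 9:

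- Tables 2.5 and 2.6 summarise chemistry values and changes from baseline. No laboratory table by grade is planned.
- Listings 20 and 21 depend on liver stopping events, which Protocol 7.1.1 and Appendix 5 define by ALT.
- Listings 22 and 23 are the only chemistry displays tied to toxicity. Listing 22 shows chemistry with any toxicity; Listing 23 shows all chemistry for the participants concerned. They are also the only participant-level chemistry listings planned.

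Two links in that last step are inferences. The SAP does not define what counts as a toxicity for inclusion, and the LB5A shell, which would show whether the grade is printed, is not in the documents.

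**Step 4: frequency.** The documents give no rate of direct bilirubin above ULN. Purely as an assumption, let p be the chance that a participant has at least one such value in the listed data, with 16 participants (the planned number) and independence between them. The chance of at least one affected participant is 1 − (1 − p)^16:

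| Assumed p | Chance of at least one affected participant |
|---|---|
| 1% | 15% |
| 2.5% | 33% |
| 5% | 56% |
| 10% | 81% |

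The result follows the assumed input and rules out little, so no frequency is claimed.

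**The case against.** The strongest reply is that this is a disclosed convention. The rules stand in the same paragraph as the general statement that DAIDS is used, and they qualify it openly. Direct bilirubin is the only row with a numeric criterion on which Rule 2 acts, which suggests that the sentence was written for it as a deliberately cautious choice. That stands. A reader might infer that the SAP contradicts itself, but a specific rule that openly qualifies a general one is a prespecified convention. What remains is that, for this row, the convention produces a severity grade that the printed criteria do not support.

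A second reply is that above ULN is not a numeric criterion, so direct bilirubin would simply go ungraded. On that reading Rule 2 would have no numeric criterion anywhere in the table to act on, which is implausible.

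A third reply is that over-inclusion is the safer error for a liver parameter. That also stands, and it limits the remedy. Taking these values out of Listings 22 and 23 would leave a participant whose only abnormality is raised direct bilirubin with no individual chemistry value in any planned display.

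Finally, one might try to restore Grades 3 and 4 by matching adverse events to samples. Someone would have to decide which events are signs of hepatotoxicity and which samples they belong to. That is adjudication, and the liver follow-up forms in Protocol Appendix 5 are triggered only by ALT ≥ 3 × ULN.

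**Conclusion.** The point holds as a minor one. Read as written, the two rules make every direct bilirubin above ULN a programmed Grade 4 and leave Grade 3 unreachable, while the printed row gives an isolated elevation no grade. Confidence is high for the rule logic. It is lower for the effect on the listings, which assumes that a programmed grade counts as a toxicity and, for the printed label, that LB5A shows grades. The frequency is unknown.

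A reader might infer that the rule could have stopped a participant's dosing or excluded someone, because Protocol 7.1.4 names Grade 4 laboratory abnormalities and Exclusion 13 uses laboratory grades. The documents do not support this. Those are decisions made during conduct, and no text ties them to the SAP's programmed grade. At most, a printed Grade 4 could be misread later as a stopping criterion that was not applied. No summary table or PK result changes either, and the output set is already abbreviated because the study ended early (SAP 1).

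**What to change.** In SAP 10.6.1, exempt direct bilirubin from both rules and flag values above ULN as High with no programmed grade. State that the flag is enough to keep the value in Listing 22 and the participant in Listing 23. Add a footnote to both listings: Grades 3 and 4 for direct bilirubin need the clinical component of the printed row, for which the reader is referred to the adverse event listings. Do not remove values from the listings, and do not derive Grade 3 or 4 by linking adverse events to samples. Leave all other rows as they are.

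The cost is a short SAP edit, one programming exception and one footnote, with no new data or adjudication. The downside is that the toxicity listings will contain a flagged value without a grade, and direct bilirubin is no longer graded automatically.

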10.7. Appendix 7: Values of Potential Clinical Importance**10.7.1. ECG**

ECG Parameter	Units	Potential Clinically Important Range	
		Lower	Upper
Absolute			
Absolute QTc Interval	msec	<320	>450
Absolute PR Interval	msec	< 120	> 200
Absolute QRS Interval	msec	< 60	> 120
Change from Baseline			
Increase from Baseline QTc	msec		> 60

10.7.2. Vital Signs

Vital Sign Parameter (Absolute)	Units	Potential Clinically Important Range	
		Lower	Upper
Systolic Blood Pressure	mmHg	< 85	> 140
Diastolic Blood Pressure	mmHg	< 45	> 90
Heart Rate	bpm	< 40	> 100

CONFIDENTIAL

209713

10.8. Appendix 8: Abbreviations & Trade Marks

10.8.1. Abbreviations

Abbreviation	Description
ADaM	Analysis Data Model
AE	Adverse Event
ANOVA	Analysis of Variance
AUC	Area under the Plasma Concentration-Time Curve
AUC(0-∞)	AUC from Time 0 Extrapolated to Infinity
AUC(0-t)	AUC from Time 0 to Time t
BA	Bioavailability
CDISC	Clinical Data Interchange Standards Consortium
CI	Confidence Interval
CL/F	Apparent Oral Clearance
C _{max}	Maximum Observed Concentration
C-SSRS	Columbia Suicide Severity Rating Scale
CV	Coefficient of Variation
CV _b	Coefficient of Variation (Between)
DAIDS	Division of AIDS
DBF	Database Freeze
DBR	Database Release
DP	Decimal Places
ECG	Electrocardiogram
eCRF	Electronic Case Record Form
GSK	GlaxoSmithKline
HLGT	High Level Group Term
ICH	International Conference on Harmonization
IDSL	Integrated Data Standards Library
LLN	Lower Limit of Normal
MedDRA	Medical Dictionary for Regulatory Activities
PK	Pharmacokinetic
PT	Preferred Term
QTcB	QTc using the Bazett formula
QTcF	QTc using the Fridericia formula
RAP	Reporting & Analysis Plan
SAC	Statistical Analysis Complete
SAE	Serious Adverse Event
SD	Standard Deviation
SDTM	Study Data Tabulation Model
SMQ	Standardized MedDRA Query
SOC	System Organ Class
t _{1/2}	Apparent Terminal Phase Half-life
t _{lag}	Lag Time for Absorption
T _{max}	Time of Maximum Observed Concentration
ULN	Upper Limit of Normal

CONFIDENTIAL

209713

Abbreviation	Description
Vz/F	Apparent Volume of Distribution

10.8.2. Trademarks

Trademarks of the GlaxoSmithKline Group of Companies
NONE

Trademarks not owned by the GlaxoSmithKline Group of Companies
SAS
WinNonlin

CONFIDENTIAL

209713

10.9. Appendix 9: List of Data Displays

10.9.1. Data Display Numbering

The following numbering will be applied for RAP generated displays:

Section	Tables	Figures
Study Population	1.1 to 1.4	
Safety	2.1 to 2.15	2.1
Pharmacokinetic	3.1 to 3.7	
Section	Listings	
ICH Listings	1 to 32	
Other Listings	33 to 34	

